5.10.2.3 Modified Cycle Analysis

In the modified cycle analysis, the definitions of expected non-bleeding and expected bleeding periods are strictly followed, i.e., all bleeding episodes that overlap with expected non-bleeding intervals are considered unscheduled. Thus in this analysis, the definitions of scheduled and unscheduled bleeding/spotting episodes presented in the Table 2 are also applicable, but early and continued withdrawal bleedings are regarded as unscheduled.

Therefore, in the derivation of endpoints where early and continued withdrawal bleeding are classed as unscheduled bleeding the following rules are used to classify each bleeding only episode, spotting only episode or bleeding/spotting episode as scheduled or unscheduled:

The episode is defined as unscheduled, if any of the following criteria are met:

- The episode has a start date after Day 7 of Cycle 1 and an end date that is on or before Day 24 of Cycle 1
- For Cycles 2 to 13, the episode has a start date after Day 3 of the cycle and an end date that is on or before Day 24 of the cycle
- The episode has a start date after Day 24 of the cycle and an end date that is after Day 3 of the next cycle (continued withdrawal bleeding/spotting)
 - Note it is not possible to have continued withdrawal bleeding for Cycle 13 because data are not collected for Cycle 14
- The episode has a start date before Day 24 of the cycle and an end date that is on or after Day 25 (early withdrawal bleeding/spotting)

The episode is defined as scheduled (withdrawal bleeding and/or spotting), if the following criterion is met:

• The episode has a start date after Day 24 of the cycle and an end date that is on or before Day 3 of the next cycle

All bleeding days and spotting days will then be classified as scheduled or unscheduled based on whether the bleeding or spotting days are included in a scheduled or unscheduled episode in the same way as outlined for the classical analysis but using the rules in this Section above where early and continued withdrawal bleeding are classed as unscheduled episodes.

5.10.3 Reference Periods (RPs)

No additional definitions other than those displayed in Table 1 were used for the reference period analysis.

5.10.4 Bleeding Endpoints for the Cycle Analysis

For the cycle analysis, the evaluable cycles will be determined as described in Section 5.1 for each subject, missing data rules are provided in Section 5.15.2 and definitions of terminology are provided in Section 5.10.1 and 5.10.2.

Depending on the approach used for the cycle analysis (the classical approach versus the modified cycle analysis), for each evaluable cycle for each subject, the following will be determined:

• Whether there was at least one unscheduled bleeding only, spotting only or bleeding/spotting episode within that cycle (see Section 5.10.2 for definition). It will be assumed that there is at least

one unscheduled episode during the cycle if there is an unscheduled episode that starts in the cycle of interest

- Whether there was at least one unscheduled bleeding only episode within that cycle (see Section 5.10.2 for definition) and no unscheduled bleeding/spotting episodes and no unscheduled spotting only episodes. It will be assumed that there is at least one unscheduled bleeding only episode during the cycle if there is an unscheduled bleeding only episode that starts in the cycle of interest
- Whether there was at least one unscheduled spotting only episode within that cycle (see Section 5.10.2 for definition) and no unscheduled bleeding/spotting episodes and no unscheduled bleeding only episodes. It will be assumed that there is at least one unscheduled spotting only episode during the cycle if there is an unscheduled spotting only episode that starts in the cycle of interest
- Whether there is an absence of any bleeding or spotting (i.e. all days in the cycle are bleeding/spotting-free days)
- Whether there is an absence of scheduled bleeding only, spotting only and bleeding/spotting episodes (i.e. there is no scheduled episode with a start date during that cycle of interest)
- Whether there is early withdrawal bleeding or spotting in that cycle (i.e. there is either an early withdrawal bleeding only, spotting only or bleeding/spotting episode that starts during the cycle of interest)
- Whether there is continued withdrawal bleeding or spotting in that cycle (i.e. there is either a continued withdrawal bleeding only, spotting only or bleeding/spotting episode that starts during the cycle of interest)
- The total (scheduled + unscheduled) number of days with bleeding and/or spotting (i.e. the number of bleeding days + the number of spotting days within the bleeding only, spotting only and bleeding/spotting episodes that start during the cycle of interest)
- The total (scheduled + unscheduled) number of days with bleeding only (i.e. the number of bleeding days within the bleeding only and bleeding/spotting episodes that start during the cycle of interest)
- The total (scheduled + unscheduled) number of days with spotting only (i.e. the number of spotting days within the spotting only and bleeding/spotting episodes that start during the cycle of interest)
- The number of unscheduled days with bleeding and/or spotting (i.e. the number of bleeding days + the number of spotting days within the unscheduled bleeding only, spotting only and bleeding/spotting episodes that start during the cycle of interest)
- The number of unscheduled days with bleeding only (i.e. the number of bleeding days within the unscheduled bleeding only and bleeding/spotting episodes that start during the cycle of interest)
- The number of unscheduled days with spotting only (i.e. the number of spotting days within the unscheduled spotting only and bleeding/spotting episodes that start during the cycle of interest)
- The number of scheduled days with bleeding and/or spotting (i.e. the number of bleeding days + the number of spotting days within the scheduled bleeding only, spotting only and bleeding/spotting episodes that start during the cycle of interest)
- The number of scheduled days with bleeding only (i.e. the number of bleeding days within the scheduled bleeding only and bleeding/spotting episodes that start during the cycle of interest)
- The number of scheduled days with spotting only (i.e. the number of spotting days within the scheduled spotting only and bleeding/spotting episodes that start during the cycle of interest)
- The start day for any scheduled bleeding episodes that have a start date within the cycle (if there are more than one scheduled bleeding episodes in the cycle, then only the start day of the earliest episode will be used)

5.10.5 Bleeding Endpoints for Analyses by RP

For the analyses by RP, the evaluable RPs will be determined as described in Section 5.1.2 for each subject, missing data rules are provided in Section 5.15.2 and definitions of terminology are provided in Section 5.10.1.

The following variables will be derived for each evaluable RP and subject:

- The total number of days with bleeding and/or spotting (i.e. the number of bleeding days + the number of spotting days within the bleeding only, spotting only and bleeding/spotting episodes that start during the RP of interest)
- The total number of days with bleeding only (i.e. the number of bleeding days within the bleeding only and bleeding/spotting episodes that start during the RP of interest)
- The total number of days with spotting only (i.e. the number of spotting days within the spotting only and bleeding/spotting episodes that start during the RP of interest)
- The number of bleeding and/or spotting episodes
- The mean duration of the bleeding and/or spotting episodes
- The number of bleeding and/or spotting free episodes
- The mean duration of the bleeding and/or spotting free episodes

For the number of bleeding and/or spotting episodes in the RP, the number of episodes is defined as the number of bleeding only episodes + the number of spotting only episodes + the number of spotting/bleeding episodes with a start date during that RP. The duration of an episode is derived as the end date of the episode – start date of the episode + 1. The mean duration of episodes in the RP is derived from the duration of all episodes with a start date during that RP. The full duration of each of the episodes is used in the derivation of the mean duration, even if the episode continues beyond the end of the RP.

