5.0 Definitions

5.1 Cycle

The expected duration of a cycle is 28 days. A 28-day cycle consists of 24 days of active tablet intake followed by 4 days of inactive tablet intake and subjects who complete the study are expected to have completed thirteen 28-day cycles.

All cycles will be determined using the start dates recorded in the diaries. The first day of a cycle is the start date recorded on the diary for that cycle and the last day of a cycle coincides with the day before the start date recorded on the diary for the next cycle. However, because the last cycle of use has no start date for a following cycle, the last day of the cycle will be assumed to be the date of last dose of study medication, whether this is an active or inactive tablet. The date of last dose of study medication in the last cycle will be derived from the data collected in the diary.

If the conception is confirmed to be during a specific cycle in the narrative and this cycle is not in the diary data, then the cycle will be included as cycle in the exposure for the derivation of the Pearl Index. If the cycle in which conception occurred is not known, cycle(s) up to the one in which the positive pregnancy test occurred will be included in the exposure for the derivation of the Pearl Index.

For the analysis of bleeding data, the cycle will be shifted by 3 days with the 3 days of the next cycle included in the previous cycle. For example, in the bleeding analysis Cycle 2 will be from Day 4 of Cycle 2 to Day 3 of Cycle 3 inclusive.

The start and stop times of a cycle will be determined before determining whether the cycle is evaluable for the Pearl Index or evaluable for the bleeding data. Data review meetings may be held to determine if cycles are at-risk cycles for the Pearl Index and if they are evaluable for the bleeding analysis prior to database lock (see Section 8.3) if the classification is not clear from the data collected and the rules in the SAP.

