5.1.2 Evaluable Cycle and Reference Period for Bleeding Data

Bleeding data will be analyzed by cycle and by 91-day reference period (RP). For the analysis of bleeding data by cycle, the cycle will be shifted by 3 days with the 3 days of the next cycle included in the previous cycle. For example, in the bleeding analysis Cycle 2 will be from Day 4 of Cycle 2 to Day 3 of Cycle 3 inclusive. For the 3 days after Cycle 13, the last non-missing response for bleeding in Cycle 13 will be imputed.

In determining whether a cycle is evaluable for the bleeding analysis of a specific population, the cycle based on the diary data will be used rather than the shifted cycle used to present the data.

For the ITT analysis, a cycle will be considered non-evaluable if:

• The length of the cycle is longer than 28 days.

A cycle will be considered non-evaluable in the per-protocol (PP) analysis for bleeding data if any of the following criteria are met:

- 1. A subject becomes pregnant in that cycle or prior to that cycle
- 2. The length of the cycle is shorter than 22 days or longer than 28 days
- 3. A subject did not have a hormone-free period towards the end of the cycle (i.e. there are not at least 4 days where an active tablet was not taken between the last day an active tablet was taken in this cycle and the first day an active tablet was taken in the next cycle)
- 4. The subject received unauthorized concomitant medication (see section 9.4.6.1 of the protocol) thought to have the potential to impact the bleeding analysis for at least one day during the cycle
- 5. Use of unauthorized pre-treatment and concomitant medication thought to have the potential to impact the bleeding analysis, if cycle starts within 28 days after discontinuation of unauthorized medication
- 6. The subject had a positive test for chlamydia or gonorrhea during that cycle
- 7. The subject missed 4 or more days of active pills during the cycle
- 8. The subject missed 2 or more consecutive days of active pills during the cycle
- 9. The subject had a procedure to the vagina, cervix or endometrium during the cycle

A cycle with missing diary bleeding data will still be considered evaluable if the criteria above are not met and bleeding data can be imputed for days with missing data (see Section 5.15.2 for details).

Three other analyses of bleeding data will be performed as follows:

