- 1. Using cycles in which all active pills were taken as per the instructions in the protocol. In this analysis, evaluable cycles will be defined as per the PP analysis but cycles where there was at least 1 day between Day 1 and Day 24 where an active pill was not taken will be excluded.
- 2. Using cycles in which exactly 1 active pill was missed. In this analysis, evaluable cycles will be defined as per the ITT analysis but only cycles where there was exactly 1 missed active pill between Day 1 and Day 24 are included.
- 3. Using cycles in which at least 2 active pills were missed. In this analysis, evaluable cycles will be defined as per the ITT analysis but only cycles where there were at least 2 missed active pills between Day 1 and Day 24 are included.

In addition, an analysis by RP will be performed where there are 4 91-day RPs defined as follows:

- RP1 = Day 1 to Day 91
- RP2 = Day 92 to Day 182
- RP3 = Day 183 to Day 273
- RP4 = Day 274 to Day 364

where Day 1 is the first day of Cycle 1 reported in the subject diary and then the remaining days are fixed using Day 1 as a reference. For example, Day 91 is 90 days after the date of the first day of Cycle 1.

A RP will be considered to be non-evaluable in the ITT analysis when the RP is less than 91 days in duration (i.e. where the subject withdraws from the study during the RP). If there are any gaps between cycles in

terms of date within the RP (i.e. at the end of the 4-day inactive pill period of a given cycle, the subject does not directly restart with the first active pill of the next pill pack), then the RP will be excluded from the ITT Population. For example, if Cycle 1 Day 28 is 1 February 2018 and Cycle 2 Day 1 is 3 February, then RP1 will be excluded from the ITT.

A RP with missing bleeding diary data will still be considered evaluable if the criteria above are not met and bleeding data can be imputed for days with missing data (see Section 5.15.2 for details).

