9.5.3.2 Reference Period Analysis

All RP analysis will be performed in the ITT Population only. The following information will be summarized for bleeding and spotting for the **RP analysis**:

- Descriptive statistics (e.g., mean, SD, median, minimum, and maximum) for the number of days of bleeding and/or spotting, bleeding only, and spotting only within a RP.
- Descriptive statistics for the number of bleeding and/or spotting episodes in each RP
- Descriptive statistics for the mean duration of the bleeding and/or spotting episodes in each RP
- Descriptive statistics for the number of bleeding and/or spotting free episodes in each RP
- Descriptive statistics for the mean duration of the bleeding and/or spotting free episodes in each RP

Note that the denominator for the percentages listed above will be the number of subjects with an evaluable RP.

The number of subjects with evaluable reference periods for each population will be summarized by reference period. The inclusion of reference periods in ITT Population will be listed by subject and reference period along with reasons for exclusion of the reference period.

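### Bleeding days in a 91-day reference period are assigned by where the episode starts, so some days are counted in the wrong period and some in none

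*SAP*

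**What the plan says.** SAP 5.1.2 fixes four RPs of 91 calendar days from the first day of Cycle 1, for example "RP2 = Day 92 to Day 182". An RP is non-evaluable if the woman withdraws before its 91 days are complete, or if there is a date gap between packs inside it.

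SAP 5.10.5 derives the RP day counts, for evaluable RPs, from the days "within the bleeding only, spotting only and bleeding/spotting episodes that start during the RP of interest". It gives no rule for cutting an episode at the end of the RP. For mean episode duration it says outright that the full length is used "even if the episode continues beyond the end of the RP". SAP 9.5.3.2 then describes the tabulated quantity as the "number of days of bleeding and/or spotting, bleeding only, and spotting only within a RP", and protocol 12.6.1 describes it in the same way.

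SAP 5.10.4 applies the same rule to cycles: days "within the bleeding only, spotting only and bleeding/spotting episodes that start during the cycle of interest". On cycle length, SAP 5.1 says "The expected duration of a cycle is 28 days". For bleeding, each cycle is moved by three days, so that "in the bleeding analysis Cycle 2 will be from Day 4 of Cycle 2 to Day 3 of Cycle 3 inclusive". By contrast, the cycle endpoint for absence of any bleeding or spotting is judged on the actual days of the cycle.

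Under Table 1 in SAP 5.10.1 an episode ends only at two free days. It has no maximum length.

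**The concern.** A reader of the tables will take days in an RP to mean days that lie in it. Under SAP 5.10.5 the figure also includes days after the RP has ended, and it leaves out days in the RP that belong to an episode begun earlier. Because only evaluable RPs are derived, the rule can also drop days from the tables altogether, or bring in days from a period that was meant to be excluded.

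The women affected are those whose bleeding crosses a boundary, and prolonged episodes cross more often. The RP boundaries give no protection against this. The three-day shift that keeps a normal withdrawal bleed inside one cycle applies to cycles only. On a nominal calendar the first three RPs end at Cycle 4 Day 7, Cycle 7 Day 14 and Cycle 10 Day 21.

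**Working it through.** There is no sample-size or power figure to reproduce here. The check applies the SAP rule literally to example diaries and compares it with a count of the days lying in each period.

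**Inputs.** RP1 is Days 1–91 and RP2 is Days 92–182 (SAP 5.1.2). Shifted Cycle 2 is Days 32–59 and shifted Cycle 3 is Days 60–87, from Day 28×(c−1)+4 to Day 28×c+3 for cycle c. The example episodes are invented to show the rule.

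**Boundaries.** 91 = 3×28 + 7; 182 = 6×28 + 14; 273 = 9×28 + 21.

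**RP counts.** SAP count = all days of the episodes whose first day lies in the RP. Actual count = days lying in the RP.

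| Diary | RP1, SAP | RP1, actual | RP2, SAP | RP2, actual |
|---|---|---|---|---|
| 14 days from Day 88 (Days 88–101) | 14 | 91−88+1 = 4 | 0 | 101−92+1 = 10 |
| The same, plus 5-day bleeds from Days 25 and 53 | 5+5+14 = 24 | 5+5+4 = 14 | 0 | 10 |
| 92 days from Day 91 (Days 91–182) | 92 | 1 | 0 | 91 |

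The last row is an extreme that shows a count larger than the period. The first row needs nothing unusual beyond crossing the boundary.

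**Evaluability, using the first row.**
- RP1 has a pack gap and is excluded, while RP2 is evaluable. RP2 shows 0, so its 10 real days appear in no table.
- RP1 is evaluable, and the woman withdraws during RP2, after Day 101. RP1 shows 14, of which 10 lie in an excluded RP.

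**If truncation was intended.** The full-length sentence is explicit only for mean duration. Suppose the day counts were meant to stop at the RP end. RP1 would then be 4, but RP2 would still be 0, because no episode starts in it. The omission remains under either reading.

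**Cycle counts.** Take bleeding from Cycle 2 Day 25 to Cycle 4 Day 3, which is Days 53–87: 4 + 28 + 3 = 35 days. Under the SAP rule Cycle 2 has 35 days (actual 59−53+1 = 7) and Cycle 3 has 0 (actual 28). One episode needs at least 29 days to exceed a cycle, or 92 to exceed an RP. Fewer suffice if the period holds other bleeding: 10 earlier days plus a 19-day episode from Cycle 2 Day 25 give 29 in a 28-day cycle.

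**How often a boundary is crossed.** The documents give no episode durations. Protocol 7.2 reports 96.5% withdrawal bleeding and 16.9% unscheduled episodes from a Phase 2 study, without saying that these are per-cycle rates. Assume that they are, that unscheduled starts are uniform over the 21 days from Day 4 to Day 24, and that durations are fixed at D days. The share with an unscheduled episode crossing the Cycle 7 Day 14 or Cycle 10 Day 21 boundary is then 0.169×(D−1)/21. That is 1.6% for D = 3, 3.2% for D = 5 and 4.8% for D = 7. With variable durations (Poisson or geometric) of the same means, simulated shares ran from 1.6% to 24% and differed sharply between the Cycle 4 Day 7 boundary and the later two.

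**The case against.** The best defence is that the rule is explicit and deliberate. SAP 5.10.4 and 5.10.5 spell out the counts, and two programmers would derive the same numbers. SAP 5.10.2.2 gives each day the scheduled or unscheduled status of its episode, and the amendment list in SAP 12.1 records a move to that basis. For cycles this stands: the episode basis serves the classification, and the three-day shift already keeps ordinary withdrawal bleeding in one cycle. It does not carry over to RPs. SAP 5.10.3 adds no scheduled/unscheduled definitions there, so nothing in the RP day counts needs the episode.

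A second objection is that moving cycle days to where they fall creates its own oddity. In the classical analysis the 35-day record is continued withdrawal bleeding, so all of it is scheduled. Cycle 3 would then show 28 scheduled days, 21 of them (Days 4–24) outside the expected bleeding window, while still being flagged as having no scheduled bleed, because that flag depends on a start. Also, cycle evaluability is judged on the diary cycle but data are shown on the shifted cycle, so a few days from non-evaluable cycles would remain. Both points stand, and they are why the cycle change is optional.

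Third, prolonged bleeding stays visible elsewhere: in full-length mean duration by RP, the continued-withdrawal flag, the modified cycle analysis, the daily bar chart (actual days) and the listings. That is correct. A reader might infer that a cycle bled through is recorded as bleed-free. The documents do not support this: absence of any bleeding is judged on actual days, so Cycle 3 would fail it. Only its day count is 0.

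**Conclusion.** The point holds for the RP day counts. A stated rule gives a figure that does not match its description, and it loses or imports days when the neighbouring RP is non-evaluable. For cycles the rule has the same consequence, but it is a chosen convention with a partial rationale.

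It is a minor point. The endpoints are secondary and descriptive, SAP 9.0 plans no formal statistical analyses, and the Pearl Index does not use these counts. Effects on group means are expected to be small, while an individual woman's count can be wrong for a whole period. Counts above the period length will be rare.

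A reader might want one figure for the share of women affected. The documents do not support one. About 2% to 24% reflects assumed durations and an assumed per-cycle reading of the Phase 2 rates, and no narrower range should be quoted.

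**What to change.** In SAP 5.10.5, count each bleeding or spotting day in the RP in which it falls, for evaluable RPs only. Keep start-based attribution for the number of episodes and mean episode duration. No RP can then exceed 91 days, and the first example becomes 4 and 10.

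The cycle counts in SAP 5.10.4 may be left as they are, with a footnote that days are credited to the cycle where the episode starts. If they are changed, let each day keep its episode's scheduled or unscheduled status and count it in the shifted cycle where it falls. Leave the episode-based flags (absence of scheduled, any unscheduled, early, continued) start-based and footnote them.

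The RP change costs a wording edit and a simpler derivation, with no new data. Its small downside is that day counts and episode counts for an RP no longer refer to exactly the same episodes.
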